5.2 Sample Size Calculations

The sample size of 90 participants was selected based on the feasibility objective of the nine clinical sites recruiting an average of 10 participants in one year. The statistical properties of the study with this sample size to address each objective are:

Objective 1. A sample size of 90 participants would allow the estimation of the rate of accrual to within \pm 11.1%.

Objective 2. This sample size would allow the estimation of a treatment compliance of 0.90 with logit-based confidence limits of 0.819, 0.947.

Objective 3. This sample size would allow the estimation of visit compliance with logit-based confidence limits of 0.880, 0.980.

Objectives 4-5. This sample size will provide 85% power to detect a difference of 0.63 standard deviation units between groups with a test at the 0.05 level two-sided.

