5.1 Statistical Analysis

The statistical analyses to be employed to address each of the study objectives are:

- 1. *Recruitment: Nine clinical sites will enroll an average of ten participants per site in one year (post approval by their IRBs).* The rate of accrual will be estimated using the mean rate from all sites, with a 95% confidence interval based on an underlying Poisson distribution [80].
- 2. Treatment Compliance: At least 90% of families will continue to take the study substance as instructed. The simple proportion of treatment compliance among all families and the 95% confidence limits will be computed.
- 3. *Visit Compliance: At least 95% of families will continue to attend follow-up visits.* The simple proportion of visit compliance among all families will be computed and the 95% confidence limits, separately for the month 6 and month 12 visits.
- 4. At least a 20% higher level of plasma and/or red blood cell membrane phospholipid DHA can be achieved in the experimental treatment group in comparison with the control group. The comparison between the two treatment arms will be based on a t-test of treatment effect in an Analysis of Covariance (ANCOVA) model adjusted for the baseline level of each measure [81].
- 5. At least a 20% lower level of the major inflammatory cytokine, IL1-beta, will be achieved in the experimental treatment group in comparison with the control group. The comparison between the two treatment arms will be based on a t-test of treatment effect in an Analysis of Covariance (ANCOVA) model adjusted for the baseline level of each measure [82].

All analyses will be stratified according to whether the participant was entered into the study prenatally (i.e. during pregnancy) or was entered after birth. This adjustment will be conducted using an additional factor in a regression model or through a stratified-adjusted analysis.

Families that contribute multiple participants to a treatment group require special methods. When possible, statistical methods that consider the family as the unit of analysis will be employed, in which all family members will contribute. Where such methods are not feasible, only the first participant entered from each family will be included in the analysis.

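### The precision stated for the recruitment objective (±11.1%) is not a 95% margin; the Poisson interval the protocol itself specifies gives about ±20.7% with 90 participants

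*Protocol*

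**What the plan says.** Section 5.2 of the Protocol explains that 90 was chosen from the target of "nine clinical sites recruiting an average of 10 participants in one year", and then lists what that number delivers for each objective. For Objective 1 it states: "A sample size of 90 participants would allow the estimation of the rate of accrual to within" ±11.1%. No confidence level or formula accompanies the figure.

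The method for Objective 1 is in Section 5.1: "The rate of accrual will be estimated using the mean rate from all sites, with a 95% confidence interval based on an underlying Poisson distribution".

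The next two entries in the Section 5.2 list also concern estimation. Objective 2 reads: "This sample size would allow the estimation of a treatment compliance of 0.90 with logit-based confidence limits of 0.819, 0.947". Objective 3 reads: "This sample size would allow the estimation of visit compliance with logit-based confidence limits of 0.880, 0.980".

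**The concern.** The count (90), the distribution (Poisson) and the confidence level (95%) are all given in the protocol, so the ±11.1% can be checked without any outside assumption. A Poisson count of 90 has a relative standard error of roughly 10.5%, so a 95% margin should be about twice that. The printed figure is close to one standard error instead.

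What is at stake is how the pilot's recruitment result is expected to read. The primary outcome is the feasibility of a full-scale study (Section 1.1), and recruitment is one of the five objectives whose fulfilment leads to such a study being considered (Section 1.2.4). It is also the objective that set the sample size. Someone who relies on ±11.1% will expect the pilot to pin down accrual to about 8.9 to 11.1 participants per site-year (10 × 0.889 and 10 × 1.111). The 95% interval is appreciably wider.

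**Working it through.** **Inputs.** Expected count n = 90, from nine sites × 10 participants in one year (Section 5.2). Poisson distribution, 95% two-sided (Section 5.1). Stated precision ±11.1% (Section 5.2).

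**Attempt to reproduce ±11.1%.** No usual Poisson interval at 80% confidence or above gives it. The plain (Wald) half-width z/√90, with 1/√90 = 0.1054, is:
- 80% two-sided: 13.5%
- 90% two-sided: 17.3%
- 95% two-sided: 20.7%

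The figure does match one standard error on the log scale: exp(1/√90) − 1 = exp(0.1054) − 1 = 11.12%. Without the log transform, one standard error is 10.54%. The match suggests that the 1.96 multiplier was left out, but this is inferred from the number alone.

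**The 95% interval for a count of 90, by method.**
- Wald: 1.96/√90 = 1.96 × 0.1054 = 20.7%. In participants, 90 ± 18.6 = 71.4 to 108.6; per site-year (÷ 9), 7.9 to 12.1. Working from the site mean gives the same: 1.96 × √(10/9) = 2.07 on a mean of 10.
- Log scale: exp(±1.96/√90) − 1 = −18.7% / +22.9%.
- Square-root scale: −19.6% / +21.7%.
- Score: −18.6% / +22.9%.
- Exact: χ²(0.025; 180)/2 = 72.37 and χ²(0.975; 182)/2 = 110.63, that is −19.6% / +22.9%, or 8.0 to 12.3 per site-year.

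Every form lies between about 19% and 23%. The ratio of the Wald figure to the stated one is 20.66/11.1 = 1.86.

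**What ±11.1% amounts to.** The confidence it carries is 2Φ(0.111 × √90) − 1 = 0.708 on the plain scale and 2Φ(ln 1.111 × √90) − 1 = 0.682 on the log scale. A 95% margin of that width would require (1.96/0.111)² ≈ 312 participants (Wald), or (1.96/ln 1.111)² ≈ 347 using the log-scale upper limit.

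**Check on the neighbouring figures.** Logit limits with n = 90 and z = 1.96, where the standard error of the logit is 1/√(n·p·(1 − p)):
- Objective 2, p = 0.90: 0.8188 and 0.9471, against the stated 0.819 and 0.947.
- Objective 3, p = 0.95 (taken from the objective): 0.8804 and 0.9800, against 0.880 and 0.980.
- Objectives 4 and 5: power at a 0.63 SD difference with 45 per arm is 84.8%, against 85%.

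All of these reproduce at the conventional level. Only the Objective 1 figure does not.

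**The case against.** The strongest defence is that Section 5.2 does not print 95% beside ±11.1%. Objectives 2 and 3 are labelled there as confidence limits and Objective 1 is not, so the sentence could be read as an unlabelled standard error. On the log scale it equals one. It is true that the level is not printed, so a miscalculated 95% interval cannot be proved from the text. The defence does not rescue the sentence, though. It is worded as a margin of error, nothing calls it a standard error, Section 5.1 fixes 95% for this very estimate, and the other two estimation entries in the list are 95% limits.

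A second defence goes to importance, and it stands. The ±11.1% did not determine the sample size; the target of nine sites times ten did. No success threshold, stopping rule or analysis step uses the figure. The interval reported at the end will come from Section 5.1, which is sound.

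Three stronger readings may tempt a reader, and the documents support none of them:
- *That the trial is too small, because ±11.1% would need 312 or more participants.* The protocol never sets that precision as a requirement.
- *That the accrual conclusion will be wrong.* The planned interval is correctly specified.
- *That the accrual rate from this pilot alone decides on the full-scale study or fixes its number of sites.* Section 1.2.4 says only that such a study will be considered if the objectives, of which there are five, are met. Neither that section nor Section 3.9 derives a number of sites from it.

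**Conclusion.** The stated precision for Objective 1 is wrong as written. Under the protocol's own 95% Poisson method, 90 participants estimate the accrual rate to about ±20.7% (Wald), or −19.6% / +22.9% (exact), and not ±11.1%. The true margin is 1.86 times the stated one, so the planning sentence understates the uncertainty by nearly half.

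The conclusion rests on a count of 90 and on the Poisson assumption in Section 5.1, and it does not depend on which 95% form is chosen. The origin of 11.1% remains an inference.

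Severity is moderate: a design property of the objective that set the sample size is misreported, while the sample size and the final analysis are unaffected.

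**What to change.** Restate Objective 1 in Section 5.2 with the confidence level and a single named method. Either of these would do:

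- *With 90 participants enrolled in one year at nine sites, the exact 95% Poisson limits would be 72.4 to 110.6 participants (8.0 to 12.3 per site-year; −19.6% / +22.9%).*
- *With 90 participants enrolled in one year at nine sites, the accrual rate would be estimated to within ±20.7% (95% Wald limits, about 71 to 109 participants; 7.9 to 12.1 per site-year).*

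The two should not be combined, because the exact upper limit lies about 23% above 90 and so falls outside a ±20.7% margin. The cost is one sentence and a less favourable stated precision; the sample size, design and analysis stay as they are.

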6 ADVERSE EVENT REPORTING AND SAFETY MONITORING

6.1 Adverse Event Definitions

6.1.1 Adverse Event

An adverse event is any occurrence or worsening of an undesirable or unintended sign, symptom or disease whether or not associated with the treatment and study procedures.

Throughout the study, the investigator must record adverse events on the appropriate adverse event form, regardless of the severity. The investigator should treat participants with adverse events appropriately and observe them at suitable intervals until the events resolve or stabilize.

Adverse events may be discovered through:

- observation of the participant;
- questioning the participant;
- unsolicited complaint by the participant

In questioning the participant the questioning should be conducted in an objective manner.

6.1.2 Serious Adverse Event

For this trial, an adverse event associated with the treatment or study procedures that suggests a significant hazard, contraindication, side effect or precaution (as described below) is to be reported as a serious adverse event (SAE).

A serious adverse event (experience) or reaction is any untoward medical occurrence that:

- results in death,
- is life-threatening,
- requires inpatient hospitalization or prolongation of existing hospitalization,
- results in persistent or significant disability/incapacity, or
- is a congenital anomaly/birth defect.

Important medical events that may not result in death, be life threatening, or require hospitalization may be considered serious adverse events when, based upon appropriate medical judgment, they may jeopardize the patient and may require medical or surgical intervention to prevent one of the outcomes listed above.

6.1.3 Unexpected Adverse Event

An adverse event is considered unexpected when the nature (specificity) or severity of the event is not consistent with the risks described in the protocol or informed consent document for a particular protocol required intervention.

6.1.4 Grading Event Severity

TrialNet has adopted usage of the National Cancer Institute (NCI) Common Terminology Criteria for Adverse Events (CTCAE) and/or study-specific criteria for classification to describe the severity of adverse events.

6.2 Adverse Event Reporting and Monitoring

Adverse events will be reported to the TrialNet Coordinating Center in accordance with the TrialNet Adverse Event Monitoring Plan (see Manual of Operations). The investigator will make a determination as to the relation to therapy and severity of event. Events will be assessed and reported in accordance with the ICH Guideline For Good Clinical Practice and per the guidance of the DHHS Office for Human Research Protections (OHRP).

The adverse event case report form for the protocol must be completed for all adverse events (AE). For reporting serious adverse events (SAE), the TrialNet MedWatch Form should also be completed and faxed to the TNCC *within 24 hours of when the site was notified of the event*. This will be reviewed by the TrialNet Medical Monitor, the TrialNet Safety Committee, and the DSMB as appropriate. Deaths must be reported immediately. Event outcome and other follow-up information regarding the treatment and resolution of the event will be obtained and reported when available, if not known at the time the event is reported. The follow-up information should contain sufficient detail to allow for a complete medical assessment of the case and an independent determination of possible causality.

Adverse events will be assessed and adjudicated, if required by the TrialNet Medical Monitor. The DSMB will conduct regular safety reviews approximately every three to six months (and, as needed) of adverse events by treatment group assignment. Serious adverse events as well as adverse events leading to study discontinuation will be reviewed by the DSMB.

7 PARTICIPANT SAFETY

7.1 Expected Side Effects and Adverse Events

7.1.1 Risks due to DHA and Infant Formula

There are no known risks of DHA to the fetus. DHA has been shown to reduce the risk of pre-term delivery. The risk of pre-term delivery was reduced from 33% to 21% when provided fish oil supplementation of 2.7 g to 6.1 g of n-3 fatty acids/day [42-44].

DHA is already provided in some new infant formulas. There may be some minor digestive system discomforts from the DHA, such as burping and reflux. The control group will receive control oil from the capsules or formulas. There could be reactions to the infant formula itself (not from the DHA). These could include severe digestive system symptoms, eczema or other rashes, or other signs of food allergy. As with all infant formulas, there is a small risk of poor weight gain and growth or temporary decrease in growth.

7.1.2 Risks due to Blood Draws and Heel Sticks

There may be some pain when the needle goes into the skin. In about one out of every 10 individuals, a small amount of bleeding under the skin will produce a bruise. There is also a small risk of more serious problems, including the temporary clotting of the vein, infection of the site or significant blood loss.

7.2 Rules and Procedures for Unmasking Randomized Participants

The management of minor symptoms will be the same regardless of a participant's treatment group assignment, and TrialNet research personnel will not need to be unmasked. The participant's treatment group assignment will not be unmasked until the end of the study. If a situation arises in which it is essential for TrialNet research personnel to be unmasked in order to appropriately treat a study participant, the NIP Principal Investigator at the clinical site will contact the Coordinating Center within 24 hours of the event.

8 ETHICAL CONSIDERATIONS AND COMPLIANCE WITH GOOD CLINICAL PRACTICE

8.1 Statement of Compliance

This study will be conducted in compliance with the protocol and current Good Clinical Practices (GCP), adopting the principles of the Declaration of Helsinki, and all applicable regulatory requirements.

Prior to study initiation, the protocol and the informed consent documents will be reviewed and approved by an appropriate Independent Ethics Committee (IEC) or Institutional Review Board (IRB). Any amendments to the protocol or consent materials must also be approved before they are implemented.

8.2 Participating Centers

Participating TrialNet clinical sites must have an appropriate assurance, such as a Federal-wide Assurance (FWA) or an Unaffiliated Investigators Agreement (UIA), with the Office for Human Research Protections (OHRP), since they are actively engaged in research and provide informed consent. The protocol and consent forms will be approved by Institutional Review Boards at each of the participating clinical sites. HIPAA regulations will be followed by each participating institution in accordance with each institution's requirements.

The investigator is required to keep accurate records to ensure the conduct of the study is fully documented. The investigator is required to ensure that all case report forms are legibly completed for every participant entered in the trial.

The investigational sites participating in this study will maintain the highest degree of confidentiality permitted for the clinical and research information obtained from participants participating in this study. Medical and research records should be maintained at each site in the strictest confidence. However, as a part of the quality assurance and legal responsibilities of an investigation, the investigational site must permit authorized representatives of the sponsor(s) and regulatory agencies to examine (and when required by applicable law, to copy) records for the purposes of quality assurance reviews, audits and evaluation of the study safety and progress. Authorized representatives as noted above are bound to maintain the strict confidentiality of medical and research information that may be linked to identify individuals. The investigational site will normally be notified in advance of auditing visits.

8.3 Informed Consent

The informed consent form is a means of providing information regarding the study to a prospective participant and allows for an informed decision about participation in the study. All participants (or their legally acceptable representative) must read, sign and date a consent form prior to participation in the study, and/or undergoing any study-specific procedures.

The informed consent form must be updated or revised whenever important new safety information is available, for certain protocol amendments, and/or whenever any new information becomes available that may affect a patients' participation in the study.

Participants will be given a written consent form by qualified study personnel (the Trial or Study Coordinator and/or Investigator or other designee). These research personnel will understand the research study, and will complete any necessary courses required by their Institutional Review Board prior to implementing the consent process. The consent form for this clinical study will be reviewed with participants and the participant will be given time to review the written consent form and ask questions. Qualified personnel, as listed above, will obtain written consent prior to the initiation of study procedures. The participant will be given a copy of his or her signed consent form.

8.4 Study Participant Confidentiality

Study records with the study participant's information for internal use at the clinical sites will be secured at the study site during the study. At the end of the study, all records will continue to be kept in a secure location. Study participant data, which is for reporting purposes, will be stored at the University of South Florida Coordinating Center. Case report forms sent to the Coordinating Center will identify participants by a unique TrialNet Identification Number. The data entry system at the Coordinating Center is a secured, password protected computer system. At the end of the study, all study databases will be archived at the Coordinating Center, and the data collection forms will be electronically scanned and saved in electronic format for long-term storage. All paper copies of the forms will ultimately be destroyed after the data is transferred.

HLA genotyping is for research purposes only. Genetic material may be stored for future use with the permission of the study participant. The results of these future analyses will not be made known to the participant.

8.5 Disclosure of HLA results

Participants will be told if their infants have lower-risk HLA genes. If there is one family member with type 1 diabetes, participants will be told if the baby has higher-risk HLA genes.

8.6 Risks and Benefits

The risks of this study are presented in the informed consent form and are described in Chapter 7. There is no guaranteed benefit to participants for their participation in the study. However, infants may benefit from early diagnosis of type 1 diabetes.

9 STUDY ADMINISTRATION

9.1 Organizational Structure

This study is part of Type 1 Diabetes TrialNet, which is funded by the National Institutes of Health through R01 grant awards. Funding will cover the costs of administration and laboratory tests associated with this study during the participant's period of follow-up.

9.2 Groups and Committees

9.2.1 TrialNet Coordinating Center

The TrialNet Coordinating Center (TNCC) will provide overall leadership to the TrialNet study group to include protocol and manual preparation, development of statistical design for each study, and analysis of study results. The TNCC will also coordinate interactions among the participating TrialNet clinical centers, test laboratories including TrialNet core laboratories and other subcontract laboratories, NIDDK, and other sponsoring agencies.

9.2.2 Clinical Sites

Each Principal Investigator at the participating TrialNet clinical site will oversee all operations. The clinical sites will forward all laboratory and data collection form information to the University of South Florida Coordinating Center for analysis. Conference calls and site visits, as needed, will facilitate evaluation of the trial management.

9.2.3 TrialNet Laboratories

TrialNet core laboratories will be utilized to perform tests and assays for this trial. In addition, local laboratories will be used. All laboratory results will be forwarded to the TrialNet Coordinating Center at the University of South Florida for analysis.

9.2.4 Clinical Site Monitoring

In order to conduct this study with established research principles and ICH-GCP guidelines, there may be site visits conducted during the study to evaluate study conduct. All sites will be monitored by the Coordinating Center and appropriate TrialNet committees for patient enrollment, compliance with protocol procedures, completeness and accuracy of data entered on the case report forms (CRFs), and the occurrence and reporting of adverse events (AEs) and serious adverse events (SAEs).

9.2.5 Data and Safety Monitoring Board (DSMB)

The DSMB will meet approximately every 6 months to review efficacy issues and adverse events prepared by the Coordinating Center. All adverse events will be recorded on the adverse event forms, which will be sent to the local IRBs, per their reporting requirements, and to the Coordinating Center. The DSMB will independently evaluate whether the adverse events constitute grounds to discontinue the study.

9.3 Partnering with Industry

Martek Biosciences Corporation and Mead Johnson Nutritionals are providing the study formulations for the DHA and control for this study. Martek Biosciences Corporation is providing the capsules and Mead Johnson Nutritionals is providing the formula.

